### B1. PURPOSE OF PROTOCOL

Nitrous oxide is a well-tolerated inhaled sedative that has been used for decades in pediatric and adult populations and is largely viewed as effective and safe. In addition to analgesic effect, nitrous oxide also produces a dissociative euphoria and amnesia that could potentially improve patients' anxiety and experience of cancer care. Over the past several decades nitrous oxide has become less common due to concerns of nitrous oxide environmental exposure to the care team. There are now FDA-approved systems that allow patient self-administered nitrous oxide (SANO), and importantly, include a scavenger system to eliminate exhaled environmental nitrous oxide. These systems are rapidly being adopted throughout the US in Urology practices, but to date, there have been no studies evaluating patient outcomes and possible risks with the adjunct use of SANO. We propose a prospective, randomized, controlled trial to assess patient perceived pain and anxiety related to prostate needle biopsy with or without SANO, and the frequency of complications associated with SANO. A secondary aim will be to demonstrate that the SANO at the time of prostate biopsy does not significantly increase burden on Urologist productivity, nor increase the difficulty of operator ease in performing the prostate needle biopsy.

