#### Specific Aims:

**Aim 1:** To determine the effectiveness of Self-Administered Nitrous Oxide (SANO) in decreasing patient perceived anxiety and pain related to prostate needle biopsy.

*Hypothesis 1.1: Patients receiving periprocedural SANO will have decreased anxiety during the procedure, as measured by STAI (State-Trait Anxiety Inventory) score, situational pain catastrophizing scale (SPCS) and patient vital signs.*

*Hypothesis 1.2: Patients receiving periprocedural SANO may have a decrease in pain as measured by VAS (visual analogue scale) score and patient vital signs.*

**Aim 2:** To demonstrate that the SANO at the time of prostate biopsy does not significantly increase burden on Urologist productivity, nor increase the difficulty of performing the biopsy.

*Hypothesis 1.1: Administration of periprocedural SANO will not significantly lengthen the time of the procedure relative to local anesthetic alone.*

*Hypothesis 1.2: Administration of periprocedural SANO will result in minimal side effects for the patients and will allow the patient to drive home independently.*

*Hypothesis 1.3: Administration of periprocedural SANO will allow the operating Urologist to perform the procedure with the same ease as on those patients who do not have SANO.*

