### **Periprocedural Data Collection**

After the biopsy, the patient will be moved to the recovery room for routine post-procedure vitals as well as completion of post-procedure STAI score and Situational Pain Catastrophizing Score (S-PCS) on a tablet computer. The S-PCS was derived from the Pain Catastrophizing Scale (PCS), a validated questionnaire used to measure catastrophic thinking associated with pain. We will also question for side effects of the nitrous oxide including nausea, vomiting, dizziness, drowsiness, with an option to enter “other” as a manual entry. An additional question of whether the patient feels comfortable driving home independently will be assessed.

Patients who do not have an escort planned after their biopsy will be asked to perform two hand-eye coordination tests after completion of post-procedure surveys. First, the participants will be verbally instructed to extend one arm in front of them, and place one finger to the tip of their nose. After, the Trail-making test Part B will be administered. This test has been promulgated by the American Medical Association to screen for driving fitness. The Trails-making Part B test will ask participants to connect numbers (1-13) to letters (A-L) randomly written on a page. This test is scored according to accuracy and time required to make the connections (Joseph, 2013). If the participant is unable to accurately complete these tests, additional recovery time will be required. The participant’s performance and disposition will be included in the documentation of study procedures performed during the visit.

The urologist who performed the biopsy procedure will be provided the Operator Survey to assess the ease of procedure.

Chart review will be performed to capture any unanticipated ED visits, admissions, or office visits for the 7 days following the procedure. We will also record any phone calls that are made by patients within 7 days of procedure that pertain to procedure concerns.

Lastly, participants who completed study procedures during their prostate biopsy will be asked to complete a survey 2-10 months following the study biopsy. This brief survey is designed to understand participant’s recollection of pain and anxiety during the biopsy. The survey is estimated to take 2-3 minutes to complete.

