### Eligibility Criteria

#### *Inclusion criteria:*

- (1) Biological male
- (2) Aged 21 to 85 years
- (3) Scheduled for prostate needle biopsy
- (4) No learning disabilities
- (5) Suitable for nitrous oxide/oxygen IHS with willingness to be randomized to inhaled SANO or inhaled oxygen during the procedure
- (6) Access to an email and computer

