### Physical Location

The biopsy procedure itself will take place in the Shapiro 3 Surgical Subspecialty clinic. Medical record reviews will occur at a secure workstation at BIDMC or through BIDMC's VPN server.

The nitrous tanks will be stored in an approved gas cylinder storage rack in (Room 385) of the Shapiro Clinic for immediate usage. There is also a gas tank storage area in the Shapiro OR (close to the clinic) for additional storage. Both spaces are secured and locked off hours.

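### Events first appearing after discharge are ascertained only passively for 7 days, so the 7-day post-discharge event rate may be understated by an unknown amount.

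*Combined protocol and SAP*

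**What the plan says.** B1 (Purpose of Protocol) lists "the frequency of complications associated with SANO" among the things the trial will assess. In the Specific Aims, the second hypothesis under Aim 2 is that "Administration of periprocedural SANO will result in minimal side effects for the patients".

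**On the day.** Periprocedural Data Collection has patients questioned in the recovery room about a list of side effects, with a free-text option. B5 (Risks related to Nitrous Oxide administration) has oxygen saturation and heart rate monitored continuously and documented in REDCap.

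**After discharge.** Periprocedural Data Collection names two sources for the 7-day window:
- "Chart review will be performed to capture any unanticipated ED visits, admissions, or office visits for the 7 days following the procedure".
- A log of procedure-related calls that patients themselves place in the same period.

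B7 (Physical Location) adds that "Medical record reviews will occur at a secure workstation at BIDMC or through BIDMC's VPN server". No request for outside records is described. The only later patient contact for data is the survey at 2 to 10 months, which is described as covering "recollection of pain and anxiety during the biopsy". B5 (Reporting of Adverse Events) says to whom events are reported, but not how or over what period they are elicited.

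**The concern.** Both 7-day sources depend on something outside the study team's control: either an encounter appears in the chart that the team reads, or the patient decides to call. A patient seen at another emergency department, an urgent care clinic or by his own doctor may not appear in that chart. A problem managed at home without a call fits neither source, however far the chart reaches.

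Missed events can only lower the observed rate, which is the direction that favours the hypothesis of minimal side effects. B4 (Possible Benefits) also hopes that the study may reveal risks of SANO not yet described. Volunteered reports and recorded encounters are a weak way to find such risks once the patient has gone home. At stake is whether a low 7-day count can be read as reassurance, since the plan offers no way to tell how much was missed.

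**Working it through.** **The plan's own figure.** The documents state no complication rate and no capture rate, so there is no figure on this point to reproduce. The only input taken from the plan is the arm size of 76 (Sample Size Justification), which does reproduce. A 4-point difference with SD 8, two-sided alpha 0.05 and 80% power needs 63.77, so 64 per group by the t-test. Allowing for 15% loss, 64 / (1 − 0.15) = 75.3, so 76. Nothing below changes it.

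**Which events each source can see.**

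| Event | Source in the plan | Captured? |
|---|---|---|
| Side effect in recovery | Direct question with free text | Yes, actively |
| Low saturation or heart rate change during the procedure | Continuous monitoring | Yes, actively |
| Unplanned visit or admission at the site within 7 days | Chart review | Yes |
| Care elsewhere, patient calls the clinic | Call log | Yes |
| Care elsewhere, no call | Chart review, if the chart shows it | Not stated |
| Problem managed at home, no call | None | No |

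The gap is confined to the last two rows.

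**Illustrative size.** Assumptions, none of them from the documents: a true 7-day post-discharge rate p, and a fraction s of those events captured, taken as 70% to 90% with lower values shown for range.

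1. Observed rate = p × s. For p = 5%: 5% × 0.9 = 4.5%, and 5% × 0.7 = 3.5%. Expected events in 76 patients fall from 76 × 0.05 = 3.8 to 3.4 and 2.7.
2. Chance of seeing no events = (1 − p × s)^76. For p = 5%: 2.0% with full capture, 3.0% at s = 90%, 5.5% at s = 75% and 14.6% at s = 50%.
3. If no post-discharge events are seen in 76 patients, the one-sided 95% upper bound solves (1 − p × s)^76 = 0.05, so p = [1 − 0.05^(1/76)] / s = 0.03865 / s.

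| Capture s | Upper bound for p |
|---|---|
| 100% | 3.9% |
| 90% | 4.3% |
| 75% | 5.2% |
| 70% | 5.5% |
| 50% | 7.7% |

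4. Between arms: with the same s in each arm, the risk ratio (p1 × s) / (p0 × s) is unchanged and the risk difference shrinks by the factor s. For an assumed 10% versus 5%, the difference is 5.0 points with full capture and 5.0 × 0.75 = 3.75 points at s = 75%. Power for that contrast with 76 per arm is 21% and 17% respectively, so the trial could not settle it in either case.

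**The case against.** The strongest reply is that the plan already looks for the effects that matter for this gas. B2 describes elimination within 2 to 3 minutes. The named side effects are asked about in recovery, saturation and heart rate are watched throughout, and patients without an escort take coordination tests before leaving. A reader might infer that the whole complication frequency in B1 is understated. The documents do not support that: same-day effects are actively sought, and only events first appearing after discharge are exposed.

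A reader might also infer that under-counting is certain. That does not follow either. The documents do not say whether the chart shows outside encounters; B7 says where records are viewed, not what they contain. A patient treated elsewhere may still call, and that call is logged. No share of care sought elsewhere is given. The Figure 1 flowchart and the survey forms were not available for this check, although the prose suggests no day-7 contact.

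Further, the plan describes the 7-day data concretely as encounters and calls, and Data Analysis does not name them as a safety rate. Its practicality measure is post-biopsy side effects and ability to drive home.

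These points narrow the concern but do not remove it. The protocol chose a 7-day window and made complication frequency a purpose of the trial, and a problem managed at home without a call has no route into the data.

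**Conclusion.** The point holds for post-discharge events only. Their 7-day ascertainment is passive, and the resulting rate may be understated by an amount that the documents do not allow anyone to estimate. With assumed capture of 70% to 90%, a zero count in 76 patients would support an upper bound of 5.5% to 4.3% instead of 3.9%. That range illustrates the mechanism and is not an estimate for this trial.

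It would be tempting to read this as a bias in the comparison of arms. The documents do not support that: patients are not told their allocation and the same sources serve both arms, so capture is probably similar. The effect is then mainly on the absolute rates and the risk difference. The primary anxiety and pain outcomes and the sample size are untouched. This is a worthwhile improvement, not a flaw that threatens the trial.

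**What to change.** Send every randomised patient one automated REDCap email at day 7, worded identically in both arms. It should ask whether he has sought care at any site since the procedure and whether he has had any problem since then. "Access to an email and computer" is already an inclusion criterion, and emailed REDCap questionnaires are already in use.

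Report events from the chart, from calls and from the survey only, separately and combined, by arm, with the response rate and exact confidence intervals. Keep self-reported symptoms distinct from healthcare encounters, so that the survey does not widen an encounter outcome unnoticed.

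If the survey is not added, label the 7-day figures as encounters recorded at the site and patient-initiated calls, and do not present them as the full complication frequency.

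The cost is one short form and one extra message per patient, with no extra staff and no change in sample size. The downsides are some non-response, so the count may still be incomplete, and self-reports that are unverified.

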### **Randomization**

Subjects will be randomized 1:1 to either SANO (treatment) or oxygen (placebo control) after completion of baseline assessment. The results of the randomization will not be disclosed to patients as part of the study (patient-blinded). The randomization module in REDCap will be used to implement randomization of the subject to our two study groups.

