### **Periprocedural Intervention**

The patient will be moved to the biopsy room and standard procedure for lateral positioning and explaining prostate biopsy will be done in the routine manner preferred by the individual Urologist. Oxygen saturation monitor will be applied to the patient's finger and monitored throughout the procedure. The patient's heart rate will also be monitored accordingly.

The inhalation gas mask will be positioned on the patient's face, and the patient will then be instructed to begin breathing as previously instructed. Initially the patient will receive 100% oxygen at 10 Liters/minute. In the control group, this will be continued throughout the procedure.

After the Urologist describes the procedure, the SANO group will have nitrous oxide turned on to 30%, ensuring that the patient is relaxed but still conversant through the procedure. The nitrous will be adjust up or down based on the patient's response to the question "are you feeling the nitrous" and "are you happy at this level". The range will be between 25 - 45%. This may take 2-3 minutes. Both groups will be asked these questions. Both groups will be asked to take several deep breaths before inserting the rectal probe. The prostate biopsy for both study and control participants will include the normal routine administration of local peri-prostatic nerve block using preferred technique of the individual Urologist. During the procedure, the patient and patient's oxygen saturation will be monitored by a [name], APP, or MD (separate from MD performing the procedure) and if at any point in time the patient is unhappy with gas inhalation, the observer will aid the patient in removing the mask. At the end of the procedure, the SANO group will be turned down to 0% nitrous oxide, and 100% oxygen will be administered through the mask for an additional 2-3 minutes as the patient is cleaned up and repositioned to the supine position. Assessment of the "time in" and "time out" of the procedure room will be recorded.

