### **Potential for Loss of Confidentiality**

There is a potential for loss of confidentiality for participants in the study. Protections will be implemented to mitigate this risk. As detailed in our protocol, we will use REDCap to collect patient information and questionnaires. Though REDCap is generally considered secure for the purposes of PHI, it is a web-based application and the data is accessible to study team members on their own personal computers. Access to our REDCap will only be limited to study team members who are trained in protecting PHI. . Any electronic study files or information that is not stored on REDCap will be kept on a secure directory on the BIDMC server that is only accessible to research staff.

Only summaries of group data will be reported in any publications or presentations, with no identification of individuals. These precautions should serve to protect PHI in accordance with HIPPA regulations.

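### Seven-day office visits and phone calls pass an undefined judgement before they are recorded, and the staff who make that judgement are not stated to be masked to arm

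*Combined protocol and SAP*

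**What the plan says.** Section B3.A of the combined protocol and SAP, under Periprocedural Data Collection, gives the only capture rule for the week after biopsy. For visits: "Chart review will be performed to capture any unanticipated ED visits, admissions, or office visits for the 7 days following the procedure". For calls: "We will also record any phone calls that are made by patients within 7 days of procedure that pertain to procedure concerns". No section says what makes a visit unanticipated or a call relevant, who decides, or whether that person is masked.

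On masking, the Randomization section says "The results of the randomization will not be disclosed to patients as part of the study (patient-blinded"; that is the only masking the plan describes. Under Periprocedural Intervention, nitrous oxide is turned on and adjusted in one arm only, so whoever runs the gas knows the allocation. Allocation is held in the study database ("The randomization module in REDCap will be used to implement randomization of the subject to our two study groups"). Section B5 gives study team members access to that database, and no restricted view of the arm is described.

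Section B1 lists "the frequency of complications associated with SANO" among the things the trial is to assess. The Data Analysis section names no summary or test for the 7-day events.

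**The concern.** Both conditions act before an event enters the study data. Whether an office visit was unanticipated, or a call concerned the procedure, can be a matter of opinion, and the opinion may depend on knowing the arm. A call about dizziness or tiredness might be logged more readily when the patient is known to have had nitrous oxide. It might equally be dismissed, because the background section says the gas is eliminated within minutes.

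At stake is the 7-day part of the complication frequency. If the filter is applied unequally, the arms can show a difference where there is none, or hide a real one, and the filtered counts cannot reveal which. Section B4 also hopes that the study may bring to light risks of the gas that are not yet described. A relevance filter suits that hope poorly, because an undescribed risk is the kind of event that a reader may judge irrelevant.

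**Working it through.** **Arm size.** The plan gives no figure for 7-day events, so the only stated figure used here is the arm size. Sample Size Justification gives an SD of 8, a difference of 4, alpha of 0.05 and power of 80%. A two-sided two-sample t-test needs 63.77, so 64 per group. Allowing for 15% loss, 64 / 0.85 = 75.3, so 76 per group and 152 in total. The stated figures reproduce and are not in dispute.

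**What the documents establish.**
1. Judgement is required: neither condition is defined in Periprocedural Data Collection or elsewhere.
2. Masking of the person judging is not described: the Randomization section covers patients only.
3. Some staff know the arm: Periprocedural Intervention has the gas run by arm.
4. The documents do not say whether those same staff review charts or log calls.

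Items 1 to 3 open a route to bias. Item 4 means that the route is possible, not shown.

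**Illustration of size.** The documents give neither an event rate nor a probability of being recorded, so both are assumed. Let 10% or 20% of each arm have a contact within 7 days, with no true difference.

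Expected recorded patients = 76 × true rate × share judged to qualify. The recorded ratio is the SANO share divided by the oxygen share; the true rate cancels.

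| Share judged to qualify, SANO v oxygen | Recorded at 10% | Recorded at 20% | Ratio |
|---|---|---|---|
| 0.90 v 0.60 | 76×0.10×0.90 = 6.8 v 76×0.10×0.60 = 4.6 | 76×0.20×0.90 = 13.7 v 76×0.20×0.60 = 9.1 | 0.90/0.60 = 1.5 |
| 0.80 v 0.50 | 76×0.10×0.80 = 6.1 v 76×0.10×0.50 = 3.8 | 76×0.20×0.80 = 12.2 v 76×0.20×0.50 = 7.6 | 0.80/0.50 = 1.6 |
| 0.70 v 0.60 | 76×0.10×0.70 = 5.3 v 76×0.10×0.60 = 4.6 | 76×0.20×0.70 = 10.6 v 76×0.20×0.60 = 9.1 | 0.70/0.60 = 1.17 |

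If the filter favours the other arm, the ratios invert: 1/1.5 = 0.67, 0.50/0.80 = 0.63 and 0.60/0.70 = 0.86. In patients, the false difference runs from 76×0.10×0.10 = 0.8 to 76×0.20×0.30 = 4.6.

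The table applies the same gap to every kind of contact. ED visits and admissions would probably be recorded much alike in both arms, and including them pulls the ratio towards 1.

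**If someone tested these counts.** Two binomials of 76 per arm were enumerated exactly, with equal true rates of 10% to 30% and Fisher's exact test at two-sided 0.05.
- Recording 0.8 in both arms: false-positive rate 2.4% to 3.2%.
- Recording 0.9 v 0.7 (ratio 1.29): 3.8% to 10.2%.
- Recording 0.9 v 0.5 (ratio 1.80): 8.9% to 37.1%.

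The plan specifies no such test, so these figures show only how sensitive small counts are to the filter.

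**The case against.** The case on the other side is substantial.

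- **Visits are not lost.** They are found by chart review, and the medical record exists apart from the study database. A visit left out could be recovered by a masked re-abstraction. This stands. It does not clearly extend to calls, because the protocol does not say how calls are documented.
- **Unanticipated may simply mean unscheduled.** For ED visits and admissions that is a natural reading and leaves little discretion. This stands for those two. An office visit soon after a biopsy is less clear-cut.
- **The call condition concerns the procedure, not the gas.** A call about the biopsy can qualify whichever gas was given. That is fair, but dizziness or fatigue could be assigned either way, and no criteria settle it.
- **The main gas-related data bypass the filter.** Patients, to whom the allocation is not disclosed, are asked about side effects in recovery, with an open entry. Oxygen saturation and heart rate are monitored continuously and documented. Section B5 also requires all adverse events to be reported, though it gives no collection method. This stands and confines the point to the 7-day contacts.
- **No between-arm analysis is specified.** The stated purpose can be read descriptively. This stands; the comparison is inferred from the purpose and the randomized design.

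A reader might infer that the people applying the filter are unblinded. The documents do not say so; they only fail to say that these people are masked. A reader might also infer that excluded events can never be checked, which is wrong for visits.

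**Conclusion.** The point holds as a modest weakness in how a non-primary outcome is collected. Two undefined conditions decide which 7-day office visits and calls are recorded, and nothing in the plan keeps the arm from the person deciding. Unequal filtering by arm is therefore possible and would be hard to detect from the study data.

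The size and direction of any bias cannot be estimated from the documents. The ratios of 1.17 to 1.6 rest wholly on assumed event rates and recording shares, and at the mild end they amount to less than one patient.

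It would be wrong to conclude that the trial's safety results as a whole are unreliable: the same-day side-effect questions and the saturation record do not pass through this filter. Nor is there a planned test whose error rate is compromised. The reason to act is that the remedy is cheap and serves a stated purpose of the trial.

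**What to change.** In Periprocedural Data Collection, replace the two conditional rules with a complete log. It should hold every ED visit, admission, office visit and patient phone call within 7 days, in both arms, with the stated reason and, for visits, whether the visit was already scheduled.

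Then classify each entry as unscheduled or procedure-related against short written criteria. Work from an extract that omits the arm and any mention of the gas. The classifier should be an existing team member who did not run the gas for that patient.

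In Data Analysis, add that all events and classified events will be reported by arm as descriptive secondary safety data.

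The cost is protocol wording and slightly more abstraction, with no new staff and no change to treatment, visits or sample size. Some irrelevant contacts will be logged, which is why both sets of counts should be shown. Masking may be imperfect where the reason text hints at the gas, but the full log lets the classification be checked.
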